7.1.5 Classification of Predominant Heart Rhythm During Echo

Holter data from the atrial sensing setup procedure during the implant visit will be used to determine each subject's predominant heart rhythm during the echocardiogram which is required to be performed within 48 hours of implant. The sinus node function will be categorized as normal sinus, sinus node dysfunction (sinus bradycardia, sinus tachycardia, other) or atrial arrhythmia. Subjects without visible P-waves and without evidence of atrial arrhythmias will be classified as having an indeterminate rhythm

(e.g. noisy signal, poor electrode placement). The AV conduction status will be categorized as persistent 3rd degree AV block, intact AV conduction, or other (e.g. 2nd degree AVB). The AV conduction status and sinus node function will be determined using the methods described in section 7.1.4.

7.1.6 Atrial Sensing Programming Optimization

Changes to the atrial sensing parameters prior to performing the echocardiogram and the resting periods at the 1-month and 3-month visits will be recorded on the e-CRFs. The number and proportion of subjects requiring optimization of their atrial sensing parameters prior to their echocardiograms and resting periods at the 1-month and 3-month visits will be summarized by predominant rhythm and specific parameter.

7.2 Study Subjects

7.2.1 Disposition of Subjects

The number of enrolled subjects, number of successfully implanted subjects, and number of subjects with usable Holter data at the 1-month visit and 3-month visit will be reported by study center and country.

The number and percentage of enrolled subjects exiting the study will be summarized by the subject status term on the Study Exit e-CRF.

A narrative of any subject deaths occurring during the study period will be provided in the final study report.

Furthermore, flow diagrams describing the subjects contributing to each of the primary and secondary objectives may be made.

7.2.2 Clinical Investigation Plan (CIP) Deviations

Deviations from the clinical investigation plan will be collected as deviations on the Study Deviation e-CRF. Deviations will be summarized in the final report in a table by coded category. Deviation coding will be performed by Medtronic, and the coding will be collected on the MDT Study Deviation e-CRF. The number of deviations per category, and the number and percentage of subjects with a deviation in this category will be reported.

A summary of deviations resulting from the COVID 19 pandemic may also be reported.

7.2.3 Analysis Sets

For each study objective, the subjects that contribute to the statistical analysis for that objective are defined in section 7.9.

7.3 Center Pooling

This study is expected to be conducted in approximately 20 centers in the USA and Hong Kong. Study results are not expected to differ by study center, therefore data from all centers will be pooled. There will be no minimum limit that each investigator must enroll. The maximum number of enrolled subjects per center is 30 subjects (or approximately 20% of the target sample size).

7.4 Handling of Missing, Unused, and Spurious Data and Dropouts

For each study objective, details of statistical analyses for handling possible missing data are provided in Section 7.9.

7.5 Adjustments for Multiple Comparisons

Since there are no formal hypotheses tested in this study, no adjustments for multiple comparisons will be made.

7.6 Demographic and Other Baseline Characteristics

Standard baseline and relevant medical history will be collected on the e-CRFs for all enrolled subjects. Baseline and medical history variables to be summarized include, but are not limited to: age, sex, cardiovascular history, arrhythmia history, and cardiovascular medications.

Baseline variables will be summarized for all enrolled subjects, all subjects with a successful Micra AV implant, and all subjects contributing to the primary objective (i.e., those subjects with a predominant rhythm of 3rd degree AV block and normal sinus node function during the 1-month visit).

For continuous variables, mean, standard deviation, median, minimum, and maximum will be reported. For categorical variables, frequency, and percentage will be reported.

7.7 Treatment Characteristics

There are no treatment requirements for this study and subjects will be implanted with the market released Micra AV (Model MC1AVR1). 

7.8 Interim Analyses

No interim analysis of the study objectives is planned for this study. However, the primary study objective may be evaluated once all subjects complete their 1-month visit.

7.9 Evaluation of Objectives

[figure not shown]
7.9.1 Holter Data Preprocessing

A Holter monitor will be placed on the subjects at the implant, 1-month follow-up, and 3-month follow-up study visits. The Holter monitor continuously records surface ECG, EGM, accelerometer signals, and device and Micra AV algorithm markers that are telemetered from the implanted Micra AV device. The marker channel includes the ventricular sensed and paced event markers as well as a marker indicating that the Micra AV sensed an atrial beat (A4 signal). In addition, the Holter records supplemental marker data from the Micra AV including the V-V interval, pacing mode, pacing amplitude, and atrial sensing specific settings and measurements, including A4 amplitude and mode switch status.

Figure 3 shows an example Holter recording for three cardiac cycles indexed by P-wave. The top line shows the ECG, the middle line displays the accelerometer signal, and the bottom line displays the Micra AV pacing markers including the AM (atrial sense) and VP (ventricular pace) markers. The supplemental markers are sent to the Holter monitor separately from the pacing markers and are indicated by a dashed arrow after the VP marker. The time from the P-wave on the ECG to the ventricular event marker can be used to determine if a ventricular beat is synchronous or not (i.e., ventricular event follows P-wave by no more than 300 ms); the presence of an atrial sense marker following a P-wave can be used to determine if an atrial contraction (A4) was detected. The pacing mode is uplinked to the Holter in the supplemental markers and indicates the pacing mode on the ventricular beat following the one associated with the supplemental marker. Therefore, it is necessary to look back to the supplemental marker prior to the P-wave to assess the ventricular pacing mode associated with the current P-wave. Measurements of the accelerometer signals (A3 and A4 amplitudes and times) are uplinked in the supplemental marker following the P-wave.

Loss of communication between the Holter monitor and the implanted Micra AV, called telemetry dropout, can lead to loss of the pacing markers, supplemental markers, or both. The times from the P-wave to the preceding marker and supplemental marker will be computed. Telemetry dropout can also be determined by a signature in the EGM and accelerometer waveforms. Telemetry dropout is implied if time to these preceding markers exceeds the time to the preceding P-wave.

[figure not shown]
Figure 3: Example Holter Recording Showing Three Cardiac Cycles

Each Holter dataset will be reviewed by Medtronic personnel experienced in the review of Holter recordings to determine the recording time, quality of the recording, and confirm correct Micra AV feature operation.

The Holter data is preprocessed to generate two spreadsheets that are used for the analyses of many of the study objectives (Figure 4). These preprocessing steps are described in subsequent sections.

[figure not shown]
Figure 4: Block Diagram Illustrating Holter File Processing

7.9.2 Holter Data Processing

Each Holter recording is stored on an SD card in a single file named flash.dat. A PC-based utility (HolterManager, NorthEast Monitoring, Inc., Maynard, MA) will be used to separate the various data types recorded on the Holter into individual files. A custom Matlab program will read these files and create two separate Matlab data files containing a collection of variables for further processing. The two channels of surface ECG will be stored in one file for P-wave truthing (note that this file does not contain Micra AV pacing or supplemental markers). Surface ECG, EGM, accelerometer signals, and Micra AV pacing and supplemental markers will be stored in the other file.

7.9.2.1 P-Wave Truthing

7.9.2.2 Timeline Generation

A timeline spreadsheet will be manually generated that identifies the start and end times of various AccelAV procedure steps, such as the resting period or the atrial sensing setup. This spreadsheet will be in a .csv format, and starting with row 4 will contain the name of the procedure step in column A, the start time of the procedure step in column B, and the end time of the procedure step in column C. The start and end times are in seconds from the start of the Holter recording. There will be a separate timeline spreadsheet for each of the three visits where there is Holter recording. An example spreadsheet for a 1-month follow-up visit is displayed in Figure 5.

The approximate start times of procedure steps are recorded in an e-CRF. These times will be used to identify the region in the Holter recording corresponding to the procedure steps. These times will be further refined to exactly identify the times of the procedure steps in the Holter recording by examining data in the Holter recording itself. For example, the atrial sensing setup times can be determined from supplemental markers indicating the status of the atrial sensing setup; the approximate time of the resting period can be determined from the e-CRF and then adjusted by looking at times of programming changes, minimal activity, and a stable heart rate.

The locations of P-waves will not be used in the generation of the timeline.

Figure 5: Example Timeline File

A	B	C	D	E	F	G	H
1	1234502 -	-	Holter record	20:43			
2		start time	end time		worksheet time	Visit	
3		(sec)	(sec)				
4	Atrial sensing setup scheduled	0	0			Implant	
5	Atrial sensing setup in progress - histogram	0	0			Implant	
6	Atrial sensing setup in progress - VDI	0	0			Implant	
7	Atrial sensing setup in progress - VDD	0	0			Implant	
8	Initial VDD	126	426	20:44	20:50	1 and 3 month	
9	VDI	428	735	20:50	20:55	1 and 3 month	
10	Resting	850	2050	20:57	21:17	1 and 3 month	
11	Ambulatory	2052	86335	0:00		1 month	
12	Implant - left implant room	0	0	0:00		Implant	
13	Implant - arrive recovery room	0	0	0:00		Implant	
14	Transportation total - worksheet	0	0	0:00		Implant	
15	Transportation 1 - worksheet	0	0	22:00	22:35	1 month	automobile
16	Transportation 1 - activity log	0	0	0:00		1 month	
17	Transportation 1 - adjudicated	0	0			1 month	
18	Transportation 2 - worksheet	0	0	0:00		1 month	add type here
19	Transportation 2 - activity log	0	0	0:00		1 month	
20	Transportation 2 - adjudicated	0	0			1 month	
21	Sleep - activity log	0	0	0:00		1 month	
22	Sleep - adjudicated	0	0			1 month	

7.9.2.3 Accuracy Spreadsheet

A Matlab program will collate 1) the identified P-waves, 2) times corresponding to distinct study procedure steps from the timeline spreadsheet, 3) pacing markers, and 4) Micra AV pacing and supplemental markers into a .csv format spreadsheet, referred to below as an “accuracy spreadsheet.” The accuracy spreadsheet uses the P-wave as the fiducial marker and contains one row of information per truthed P-wave that occurred during the Holter recording. An example of the use of this spreadsheet is to compare the time from a P-wave to the next ventricular event (Column B) to 300 ms to determine if a beat was synchronous. This can be further selected to specific procedure steps (Columns K and L) to characterize the AV synchrony for a specific procedure step, such as the resting period.

Loss of communication between the Holter and the implanted Micra AV, called telemetry dropout, can lead to loss of the pacing markers, supplemental markers, or both. Presence of telemetry dropout and the duration of the dropout is provided in the spreadsheet. In addition, an indication of telemetry in the first 300 ms after a P-wave is provided so that beats with no ventricular sense or pace markers and evidence of telemetry dropout in the first 300 ms after a P-wave can be excluded from analyses. Furthermore, some analyses may rely on valid Micra AV pacing or supplemental markers from the

previous pacing cycle. The times of the preceding markers is provided in the spreadsheet and if these exceed the previous P-P interval, telemetry dropout is implied.

Figure 6 displays an example accuracy spreadsheet. The columns of the accuracy spreadsheet are defined as follows:

1. (A): Time of P-wave in seconds relative to the beginning of the Holter recording
2. (B): Time in seconds from P-wave to next ventricular event (VS or VP)
3. (C): Time in seconds from P-wave to next A4 detection
4. (D): Time in seconds between the ventricular event preceding and following the P-wave (i.e., the R-R interval)
5. (E): Marker code associated with the ventricular event following the P-wave. Codes of 160, 172, or 173 mean a VS and codes of 163 or 164 mean a VP
6. (F): Time in seconds from ventricular event preceding the P-wave to the P-wave
7. (G): Bit encoding for Micra AV algorithm settings at last supplemental marker before the current P-wave. Note Micra AV algorithm settings are decoded in columns (P) and (Q).
8. (H): Selected accelerometer vector at last supplemental marker before the current P-wave
9. (I): Presence (1) or absence (0) of telemetry dropout in the interval from the current P-wave to the next P-wave
10. (J): Duration of telemetry dropout in seconds in the interval from the current P-wave to the next P-wave
11. (K): Procedure step identifier (row of the procedure step from the timeline spreadsheet
12. (L): Procedure step decoded name (alphanumeric) corresponding to procedure step identifier
13. (M): Identifier for presence (1) or absence (0) of ventricular event (VS or VP) in the current P-wave to next P-wave cycle. Note that this is redundant with Column A (i+1) – A(i) < B(i) but simplifies calculations
14. (N): Presence (1) or absence (0) of telemetry dropout in the first 300 ms after the P-wave
15. (O): Time in seconds from the ventricular supplemental marker prior to the P-wave to the P-wave. If this interval exceeds the P-P interval then the Micra AV supplemental marker was lost to telemetry dropout.
16. (P): Micra AV algorithm mode at last supplemental marker before the current P-wave (1 = VDD/Adaptive, 3 = VDI/Monitor)
17. (Q): Pacing mode at last supplemental marker before the current P-wave (0=OOO, 1=VOO, 2=VVI, 3=OVO, 4=ODO, 5=VDI, 6=VDD, 10=VVIR, 13=VDIR, 130=VVI40)
18. (R): Time in seconds from current P-wave to the next ventricular supplemental marker following the P-wave

19. (S): A4 maximum amplitude in ADC counts
20. (T): Time in seconds to A4 maximum from prior ventricular event
21. (U): A3 maximum amplitude in ADC counts
22. (V): Time in seconds to A3 maximum from prior ventricular event

Figure 6: Example Holter Data (Accuracy Spreadsheet)

	A	B	C	D	E	F	G	H	I	J	K	L	M	N	O	P	Q	R	S	T	U	V
1	P time (s)	P-V time (s)	P-A4 time (s)	R-R time (s)	V type	P-priorV	enables	vector	tel	dropout	tel	duration	procedure	VSVP	In P tel	dropo	prior	Vsupp	I	A4 max in A4 max in A3 max in A3 max time		
12367	8334.317	0.7	1.622	1.203	163	0.503	253	3	0	0	8	Resting	1	0	0.467	1	6	0.719	21	0.781	51	0.578
12368	8335.05	0.903	0.888	0.936	163	0.038	253	3	0	0	8	Resting	0	0	0.014	1	6	0.922	52	0.914	45	0.555
12369	8335.739	0.214	0.2	0.939	163	0.722	253	3	0	0	8	Resting	1	0	0.703	1	6	0.233	52	0.914	45	0.555
12370	8336.45	0.639	1.611	1.136	163	0.497	253	3	0	0	8	Resting	1	0	0.478	1	6	0.678	21	0.711	49	0.568
12371	8337.128	0.947	0.933	0.986	163	0.039	253	3	0	0	8	Resting	0	0	1.156	1	6	0	21	0.711	49	0.563
12372	8337.878	0.197	0.183	0.986	163	0.769	253	3	0	0	8	Resting	1	0	0.75	1	6	0.247	49	0.977	43	0.555
12373	8338.567	0.64	1.614	1.136	163	0.492	253	3	0	0	8	Resting	1	0	0.442	1	6	0.681	21	0.773	57	0.57
12374	8339.25	0.944	0.931	0.983	163	0.039	253	3	0	0	8	Resting	0	0	0.003	1	6	0.967	38	0.961	44	0.57
12375	8339.994	0.2	0.186	0.983	163	0.783	253	3	0	0	8	Resting	1	0	0.747	1	6	0.222	38	0.961	44	0.57
12376	8340.7	0.633	1.603	1.139	163	0.506	253	3	0	0	8	Resting	1	0	0.483	1	6	0.669	21	0.727	50	0.57
12377	8341.372	0.95	0.931	0.989	163	0.039	253	3	0	0	8	Resting	0	0	0.008	1	6	0.964	47	0.984	36	0.505
12378	8342.128	0.19	0.175	0.989	163	0.794	253	3	0	0	8	Resting	1	0	0.758	1	6	0.208	47	0.984	36	0.555
12379	8342.828	0.636	1.614	1.142	163	0.506	253	3	0	0	8	Resting	1	0	0.492	1	6	0.664	22	0.766	40	0.563
12380	8343.5	0.961	0.942	0.997	163	0.036	253	3	0	0	8	Resting	0	0	0.008	1	6	0.992	39	0.992	33	0.563
12381	8344.256	0.205	0.186	0.997	163	0.792	253	3	0	0	8	Resting	1	0	0.764	1	6	0.236	39	0.992	33	0.563
12382	8344.95	0.65	3.697	1.139	163	0.489	253	3	0	0	8	Resting	1	0	0.458	1	6	0.664	26	0.766	51	0.672
12383	8345.639	2.069	3.008	2.108	163	0.039	253	3	1	0.094	8	Resting	0	0	0.025	1	6	2.097	23	0.758	31	0.57
12384	8346.367	1.342	2.281	2.108	163	0.767	253	3	1	0.316	8	Resting	0	1	0.753	1	6	1.369	23	0.758	31	0.57
12385	8347.061	0.647	1.586	2.108	163	1.461	253	3	1	0.285	8	Resting	1	1	1.447	1	6	0.675	23	0.758	31	0.57
12386	8347.744	0.914	0.903	0.95	163	0.036	253	1	0	0	8	Resting	0	1	0.008	1	6	0.928	40	0.953	69	0.555
12387	8348.467	0.192	0.181	0.95	163	0.758	253	1	0	0	8	Resting	1	0	0.731	1	6	0.206	40	0.953	69	0.555
12388	8349.161	0.639	1.625	1.142	163	0.503	253	1	0	0	8	Resting	1	0	0.489	1	6	0.667	22	0.781	46	0.578
12389	8349.833	0.972	0.953	1.006	163	0.033	253	1	0	0	8	Resting	0	0	0.006	1	6	0.992	44	0.977	33	0.555
12390	8350.578	0.228	0.206	1.006	163	0.778	253	1	0	0	8	Resting	1	0	0.75	1	6	0.247	44	0.977	33	0.555
12391	8351.269	0.656	1.589	1.139	163	0.483	253	1	0	0	8	Resting	1	0	0.464	1	6	0.692	24	0.711	69	0.555
12392	8351.983	0.914	0.894	0.955	163	0.039	253	1	0	0	8	Resting	0	0	0.005	1	6	0.933	47	0.953	56	0.555
12393	8352.7	0.197	0.178	0.953	163	0.756	253	1	0	0	8	Resting	1	0	0.719	1	6	0.217	47	0.953	56	0.555
12394	8353.372	0.661	1.608	1.136	163	0.475	253	1	0	0	8	Resting	1	0	0.456	1	6	0.7	22	0.758	59	0.563

7.9.2.4 Ventricular Event Spreadsheet

Holter datasets will be further analyzed to extract information related to ventricular sensing (including V-V interval). Specifically, a Matlab program will collate each ventricular event, times corresponding to distinct study procedures, and other device markers and information in a .csv file, referred to below as an “VEvent spreadsheet” that will contain one row per ventricular event (i.e., ventricular pace or sense). This contrasts with the accuracy spreadsheet where each row contains information for a P-wave.

Similar to the discussion of the accuracy spreadsheet creation, loss of communication between the Holter and the implanted Micra AV, called telemetry dropout, can lead to loss of the Micra and Micra AV supplemental markers. Note that since this spreadsheet is created from ventricular pacing markers, the loss of a pacing marker can only be inferred from a long interval between ventricular events with evidence of telemetry dropout. Some analyses may rely on Micra AV pacing and supplemental markers from the previous pacing cycle. The times of the preceding markers are provided in the spreadsheet, and if these exceed the previous V-V interval, telemetry dropout is implied.

Figure 7 shows an example VEvent spreadsheet. The VEvent spreadsheet uses the ventricular event as the fiducial marker and contains one record per ventricular event that occurred during the Holter recording. The columns of the VEvent spreadsheet are defined below:

1. (A): Time of ventricular event in seconds relative to the beginning of the Holter recording
2. (B): Marker code associated with the ventricular event. Codes of 160, 172, or 173 mean a VS and codes of 163 or 164 mean a VP
3. (C): Programmed lower rate in bpm
4. (D): Time in seconds from the ventricular supplemental marker prior to the V-Event to the V-Event. The Micra AV algorithm mode and pacing mode are derived from the ventricular supplemental marker. The ventricular supplemental marker is uplinked separately after each V-Event
5. (E): Micra AV algorithm mode at last supplemental marker before the current V-Event (1=VDD/Adaptive, 3=VDI/Monitor)
6. (F): Pacing mode at last supplemental marker before the current V-Event (0=OOO, 1=VOO, 2=VVI, 3=OVO, 4=ODO, 5=VDI, 6=VDD, 10=VVIR, 13=VDIR, 130=VVI40)

8948	8356.133	163	49.87		1.125	1	6	8357.128	49.87	50	15	0	0	0	8 Resting	
8949	8357.125	163	49.87		0.961	1	6	8357.128	49.87	50	15	0	0	0	8 Resting	

7.9.3 Primary Objective

Characterize AV synchrony during rest at 1-month post-implant in subjects with persistent 3rd degree AVB with normal sinus node function.

7.9.3.1 Endpoint Definition

For each ECG confirmed P-wave that occurs during the 20-minute resting period at the 1-month visit, the endpoint will be considered met if a ventricular beat (ventricular pace or sensed event) is within 300 ms following an ECG confirmed P-wave.

7.9.3.2 Performance Requirements

There is no pre-specified performance requirement for this study.

7.9.3.3 Analysis Methods

At the 1-month study visit, a Holter monitor will be placed on the subject. Each subject's Holter monitor will record surface ECG and Micra AV markers. Specifically, the Holter will record whether the Micra AV senses an atrial contraction (A4 signal representing active ventricular filling detected by the accelerometer), delivers a pacing spike, or inhibits a pacing spike based on a sensed intrinsic R-wave. Holter files will be processed as described in Section 7.9.2.

The accuracy spreadsheet derived from each Holter file (see section 7.9.2.3) will be used to determine the synchrony status (yes or no) for each P-wave. Each accuracy spreadsheet will be imported into SAS

and/or R and the P-P interval computed for each P wave i (where $i > 1$) as the time in seconds in Column 1 (A) for the i^{th} P-wave minus the time in seconds in Column 1 (A) for the $i^{th}-1$ P-wave. Each P-wave in the accuracy spreadsheet file will be classified as being evaluable or not evaluable. P-waves that are not evaluable include:

1. P-waves with no ventricular sense or pace markers and indication of telemetry dropout in the first 300 ms after the P-wave. These are identified from the accuracy spreadsheet where column 13 (M) = 0 and column 14 (N) = 1.
2. P-waves that occur during an AV conduction mode switch for subjects with a predominant rhythm of persistent 3rd degree AV block and normal sinus node function. During an AV conduction mode switch the pacing mode is set temporarily to VVI40 while the device checks for intrinsic AV conduction. These are identified from the accuracy spreadsheet where a supplemental marker in the preceding P-P interval (column 15 (O) < P-P interval), and the pacing mode in the supplemental marker is VVI40, indicating a mode switch (column 17 (Q) = 130). Note that for the pacing mode, the supplemental marker indicates the pacing mode on the next ventricular event, which is why a look-back to the preceding supplemental marker is necessary to determine if the current ventricular event is in a mode-switched state.
3. P-waves that occur during VVI mode during the resting and ambulatory periods for subjects with a predominant rhythm of persistent 3rd degree AV block and normal sinus node function. The device may be permanently programmed to VVI or switches to VVI mode temporarily each hour to perform a pacing threshold confirmation check and once per day to perform a pacing capture threshold test. While the device is in VVI mode AV synchronous pacing is not expected to occur in these subjects. These cycles are identified from the accuracy spreadsheet where a supplemental marker in the preceding P-P interval (column 15 (O) < P-P interval), and the pacing mode in the supplemental marker is VVI40, indicating a mode switch (column 17 (Q) = 2).

All other P-waves in the accuracy spreadsheet will be considered evaluable. Evaluable P-waves will be considered synchronous if they occur within 300 ms of the following ventricular event. Thus, evaluable P-waves will be considered synchronous if column 2 (B) ≤ 0.3 and asynchronous if column 2 (B) > 0.3 .

For the analysis of the primary objective, P-waves with records in the accuracy spreadsheet for each subject's 1-month Holter file corresponding to resting period (i.e., columns 11 (K) and 12 (L) indicate resting phase) will be selected.

A logistic regression model using generalized estimating equations, to account for the fact that the Micra AV's performance may be correlated within a study subject, will be used to construct a single estimate of the rate of AV synchrony and its 95% two-sided confidence interval across all subjects. Specifically, the outcome variable will be each successful/unsuccessful synchronous beat during the approximately 20 minutes resting period at the 1-month visit and the model will contain an intercept

term and consider observations repeated across subjects with an exchangeable working correlation structure.

A sample SAS PROC GENMOD statement for computing the overall point estimate for the algorithm's ability to provide AV synchrony and its two-sided confidence interval across all subjects is displayed below:

```
proc genmod data = AVsynchData descending;
  class pt;
  model AVsynch = / dist = binomial link = logit;
  repeated subject = pt / type = exch;
  estimate 'probability of success' int 1/ alpha = 0.05;
  output out = pred p = phat;
run;
```

In the SAS code above, "pt" is the subject identifier and "AVsynch" is an identifier for whether a ventricular beat (ventricular pace or sensed event) is within 300 ms following an ECG confirmed P-wave (1=yes, 0=no). The ESTIMATE statement requests the mean probability of success and its 95% confidence interval across all subjects and beats.

Additionally, point estimates for the percentage of synchronous beats at the 1-month visit will also be calculated for each individual subject by dividing the number of synchronous beats by the total number of evaluable cardiac cycles. The median AV synchrony across point estimates for each subject will also be computed.

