#### **12.6.5. Missing Data**

Similar to the primary objective, beats with no ventricular sense or pace markers and indication of telemetry dropout in the first 300 ms following a P-wave will be excluded (i.e., they are not evaluable beats). The total number of heart beats and total number of evaluable beats will be summarized for each subject and visit combination.

Additionally, a sensitivity analysis will be performed to assess the sensitivity of the estimated difference in AV synchrony percentage with respect to the missing data. Specifically, the analysis will include in the statistical model all subjects with persistent 3rd degree AV block and normal sinus node function and at least one evaluable cardiac cycle at the 1-month and 3-month visits respectively.

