7.9.3.5 Determination of Subjects and Data for Analysis

All enrolled subjects with usable Holter data, a predominant rhythm of persistent 3rd degree AV block and normal sinus node function at the 1-month visit, and at least 500 evaluable beats during the resting period at the 1-month visit will be included. Specifically, data from the approximately 20 minute resting period at the 1-month visit will be included in the analysis of the primary objective.

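### The telemetry-dropout exclusion in SAP 7.9.3.3 depends on whether a ventricular marker was seen, so it can shift the AV synchrony percentage in either direction, probably by little

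*SAP*

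**What the plan says.** SAP 7.9.3.3 lists three kinds of P-wave that are not evaluable. The first covers telemetry loss: "P-waves with no ventricular sense or pace markers and indication of telemetry dropout in the first 300 ms after the P-wave". In terms of the accuracy spreadsheet, these are the rows with "column 13 (M) = 0 and column 14 (N) = 1".

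SAP 7.9.2.3 defines the two columns over different spans:
- Column M covers the whole cycle: "Identifier for presence (1) or absence (0) of ventricular event (VS or VP) in the current P-wave to next P-wave cycle".
- Column N covers only the decisive window: "Presence (1) or absence (0) of telemetry dropout in the first 300 ms after the P-wave".

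Everything not excluded is kept ("All other P-waves in the accuracy spreadsheet will be considered evaluable") and scored from the P-to-ventricular time: "evaluable P-waves will be considered synchronous if column 2 (B) ≤ 0.3 and asynchronous if column 2 (B) > 0.3".

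The protocol carries the same exclusion for secondary objective 1, in 12.6.5: "beats with no ventricular sense or pace markers and indication of telemetry dropout in the first 300 ms following a P-wave will be excluded". It repeats it for secondary objective 2 in 12.7.5, and both sections present it as the primary objective's handling. A subject enters the primary analysis with "at least 500 evaluable beats during the resting period at the 1-month visit" (SAP 7.9.3.5).

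SAP 7.9.3.6 requires counts of total and evaluable beats and one sensitivity analysis, which lifts the 500-beat minimum. Further methods for telemetry loss are optional and unspecified.

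**The concern.** When dropout falls in the 300 ms window (N=1), there are three possible outcomes:
- a marker seen within 300 ms: kept, synchronous;
- a marker seen later in the cycle: kept, asynchronous;
- no marker before the next P-wave: removed.

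A truly synchronous beat is removed if its marker was lost. A truly asynchronous beat is removed if its marker was lost, or if the cycle contained no ventricular event at all. The latter happens whenever the ventricle runs slower than the atrium. These two chances of removal are equal only by coincidence, so the beats that remain need not be a fair sample of the resting period.

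The synchrony percentage is the primary endpoint and also underlies secondary objectives 1 and 2. The GEE interval reflects variation between subjects and would not show such a shift. For secondary objective 1 the shift cancels only if dropout behaves alike at both visits. The required sensitivity analysis leaves the rule unchanged.

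**Working it through.** **Yardstick from the plan.** SAP Table 2 gives, for 75 subjects, a median distance of 2.9 points from estimate to lower limit and an 89.7% chance that it is below 3.5. The subject-level data behind that bootstrap are not in the documents, so it can only be approximated.
- The interval 84.8% to 92.5% gives a logit standard error of (2.512 − 1.719)/(2 × 1.96) = 0.202.
- Scaling by √(40/75) gives 0.148. Around Table 2's 88.76%, the distance is 3.2 points.
- A bootstrap from a surrogate pool of 40 values (mean 89.3%, median 93.7%) gives 3.0 points and 91.8%.

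These are close, though not a reproduction. The 3.5 points serve here only as a scale.

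**Formula.** Let p be true synchrony (0.892, SAP 7.9.3.4) and d the share of P-waves with N=1 (not given; assumed 1% to 20%). Let es and ea be the shares of truly synchronous and truly asynchronous N=1 beats that the rule removes (assumed). The expected percentage is

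p' = p(1 − d·es) / [p(1 − d·es) + (1 − p)(1 − d·ea)]

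Example with d = 0.10, es = 0.5, ea = 0: 0.892 × 0.95 = 0.8474, and 0.8474/(0.8474 + 0.108) = 0.8870, a shift of −0.50 points.

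| d | es=0.5, ea=0 | es=ea | es=0.5, ea=1 | extreme: es=1, ea=0 | extreme: es=0, ea=1 |
|---|---|---|---|---|---|
| 1% | −0.05 | 0 | +0.05 | −0.10 | +0.10 |
| 5% | −0.25 | 0 | +0.25 | −0.50 | +0.48 |
| 10% | −0.50 | 0 | +0.51 | −1.06 | +0.97 |
| 20% | −1.06 | 0 | +1.08 | −2.35 | +1.97 |

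**Simulation.** es and ea are linked, because a burst long enough to lose most early markers also loses later ones. Random bursts of 0.1, 0.3 and 1.0 s were therefore simulated. Assumed timings: P-P interval 0.75 s, synchronous events at 0.15 to 0.25 s, asynchronous events at 0.35 to 0.70 s. The share of asynchronous cycles with no ventricular event was set to 0, 0.5 or 1.

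| | d = 5% | d = 20% |
|---|---|---|
| Current rule, all settings | −0.16 to +0.37 | −0.64 to +1.50 |
| Current rule, half of asynchronous cycles without an event | +0.03 to +0.13 | +0.06 to +0.53 |
| Exclude on N=1 alone | within about 0.03 of zero | within about 0.03 of zero |

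With no exclusion at all, lost markers would count as asynchronous. At es = 0.5 that costs 0.892 × 0.05 × 0.5 = 2.2 points at d = 5%, and 8.9 points at d = 20%.

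**The SAP's own example (Figure 6, rows 12367 to 12394).** Of 28 P-waves, 8 are recorded as synchronous, all with M=1. Of the other 20, 10 have M=0. Three rows have N=1:
- **12384** (M=0, removed). It lies in an R-R interval of 2.108 s, at a lower rate near 50 bpm (about 1.2 s). Neighbouring R-R intervals alternate near 0.98 and 1.14 s, which sum to 2.12 s, so one marker was probably lost. Counting back 1.139 s from the event at 8347.708 s puts it at 8346.569 s, which is 0.20 s after this P-wave. The beat was probably synchronous.
- **12385** (M=1, kept). The ventricular event comes at 0.647 s: asynchronous.
- **12386** (M=0, removed). R-R is 0.95 s, with the next event at 0.914 s and after the next P-wave: apparently asynchronous. Its dropout columns I and J read 0 although N=1, which may be a flaw in the example or in its extraction.

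Current rule: 8/26 = 30.8%. All N=1 rows dropped: 8/25 = 32.0%. No exclusion: 8/28 = 28.6%. The first two differ by one row, so this illustrates the mechanism and says nothing about rates.

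**The case against.** The strongest defence is that the rule removes beats whose status the markers cannot settle, and keeps beats whose status was observed despite some dropout. It does not delete known failures, and it avoids the much larger downward error of scoring lost markers as asynchronous. There is no hypothesis test and no performance requirement, beat counts will be reported, and optional methods for telemetry loss are named. All of this stands, and it keeps the point minor. It does not remove the mechanism: keeping a beat only when a marker survives is still selection on the outcome's own marker.

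Excluding on N=1 alone has its own price. It discards beats of known status, and it is unbiased only if dropout is unrelated to synchrony.

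Three stronger readings are tempting and not supported:
- **That the rule inflates synchrony, because a beat recorded as synchronous is never removed.** Truly synchronous beats with lost markers are removed, so the net effect can have either sign. Figure 6 shows one probable beat of each kind removed.
- **That the percentage is biased by a known amount.** No dropout rate is given. Larger shifts need a high loss of early markers together with little loss of later ones, which long bursts do not produce.
- **That subjects near the 500-beat minimum are badly distorted.** Setting d = 0.6 with about 1,400 P-waves (assumed) and assumed removal shares of es = 0.9, ea = 0.3 or es = 0.2, ea = 0.5 leaves about 700 or 1,200 evaluable beats. Neither case is near the floor, so no figure for such subjects can be defended.

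**Conclusion.** The point holds as a minor one: rule 1 ties exclusion to the marker that defines the outcome and can bias the AV synchrony percentage upward, downward or not at all. The sign depends on burst length and on how often asynchronous cycles contain no ventricular event. Under the assumed rates, the shift is at most about 1 point when up to 10% of P-waves have N=1, even at the formula's extremes, against a target precision of 3.5 points. Realistic burst patterns usually give much less. These sizes rest on p = 89.2%, an assumed dropout share, assumed timings, and dropout occurring independently of synchrony.

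There is also an ambiguity. The verbal rule can be read as no marker in the first 300 ms, whereas column M spans the whole cycle. Row 12385 would be excluded under one reading and kept under the other. The verbal reading sets ea = 1, an upward shift of about 0.25 points at d = 5% and es = 0.5.

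**What to change.** 1. Define a P-wave as not evaluable for telemetry loss if N = 1, whatever the value of M. Make the change in SAP 7.9.3.3, 7.9.4.5 and 7.9.5.5, with matching wording in Protocol 12.6.5 and 12.7.5. This also removes the ambiguity about the marker window.
2. State the assumption: dropout in the first 300 ms is unrelated to synchrony.
3. Keep the current rule as a pre-specified sensitivity analysis.
4. Add bounds that score the excluded P-waves all synchronous and all asynchronous. In Figure 6, with three rows excluded, these are 11/28 = 39.3% and 8/28 = 28.6%. The gap between the bounds equals the excluded share, so read them as worst cases.
5. Report the share of P-waves with N=1, by visit and period.

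The cost is one condition in the program, three SAP paragraphs and two protocol paragraphs, with no new data. Some beats of known status are lost, and a few subjects may fall below 500 evaluable beats. The existing sensitivity analyses in SAP 7.9.3.6 and 7.9.4.5, which lift that minimum, cover them, as does the additional ambulatory estimate in 7.9.5.6.
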